 - (4) Change in subject specific memory, defined as the MSVT, between baseline and six months post-conversion in both arms
 - (5) Change in subject specific cognitive function, defined as the MoCA, between baseline and six months post-conversion in both arms
 - **(6)** Change in subject specific renal function, defined as the 4 variable MDRD, between baseline and six months post-conversion in both arms

5) Inclusion & Exclusion Criteria

- i) Potentially eligible patients will be screened by the PI and study coordinator using inclusion and exclusion criteria below to determine if they qualify for the study.
- ii) Inclusion criteria
 - (1) Male or female adult (≥18 years old) with a history of liver or liver/kidney transplant within 15 days to 12 months of transplant.
 - (2) Patients must be capable of understanding the purposes and risks of the study and have the ability to give written informed consent and be willing to participate and comply with the study. For those that consent virtually, subjects must be willing and able to use the Doxy.me platform and complete assessments virtually.
- iii) Exclusion criteria
 - (1) Patients will be excluded if they are pregnant or nursing females or males with a pregnant female partner
 - (2) HIV positive (HIV ab +)
 - (3) Unable to tolerate oral medications
 - (4) Use of another investigational product within thirty days prior to receiving study medication
 - (5) Moderate acute cellular rejection (RAI ≥ 5) within the past month
 - **(6)** A condition that is known to cause tremor such as essential tremor, Parkinson disease, or enhanced physiologic tremor.
 - (7) Patients taking medications known to induce tremors or dopamine blocking agents

(8) A condition or disorder that, in the opinion of the investigator, may adversely affect the outcome of the study or the safety of the subject

6) Number of Subjects

a) There will be 15 subjects in each arm, 30 subjects total

7) Setting Where Research Will Be Conducted

a) Study activities, including consent, enrollment, and randomization, will occur in the Liver Transplant Clinic at the Medical University of South Carolina or through Doxy.me.

8) Recruitment Methods

- a) Study enrollment procedures

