- i) Includes sodium, potassium, chloride, CO2, BUN, SrCr, glucose, calcium, WBC, HgB, Hct, platelets
- ii) Includes AST, ALT, alkaline phosphatase, total bilirubin, albumin, total protein
- iii) Tacrolimus concentrations will be 12- or 24-hour levels, drawn in the morning of each assessment
- iv) Only required for patients with self-reported tremor
- v) MSVT,MMSE, MoCA, FTM will be completed through a Doxy.me visit. PGI-I, IMAB-Q 10 and SF-10 will be sent to the subject through REDCap to be completed. Necessary materials (ball point pen and paper) to complete the MoCA, MMSE, and FTM will be shipped to the subject prior to the Doxy.me visit.
- vi) For subjects consented through Doxy.Me, this will be done prior to the baseline visit with the assessments.

11) Specimen Collection and Assessments

- i) Clinical and Laboratory Assessments:
 - (1) Laboratory evaluations will be performed at certified laboratories according to the study schedule. Required tests are specified in the Schedule of Evaluations. Laboratory

- specimens will not be stored for the study or sent to any outside facilities. Specimens will not be used for future research.
- (2) All subjects will undergo clinical assessment by the investigator or the investigator's designee in the manner and at the times specified in the Schedule of Evaluations
 - (a) Adverse events will be determined and defined according to the protocol
 - (b) Doses will be recorded of all immunosuppressants.
 - (c) Rejection and infection events will be recorded, as defined in the protocol
- (3) Renal function assessment will be monitored at regular intervals using the 4-variable abbreviated MDRD equation. It will be monitored at baseline and the end of the study for study outcomes and any time points dictated by standard of care follow-up in between those time points.
- ii) Definitions
 - (1) Acute rejection is defined as a liver allograft biopsy showing RAI 5 or greater, by the 1997 Banff Criteria and all updates since then. Biopsies will be performed when clinically warranted, based on changes in allograft function.
 - (2) Rejection reversal is defined as return of liver function tests to within 20% of baseline and/or histologic clearance by Banff Criteria
 - (3) Recurrent acute rejection is defined as rejection recurring more than two weeks after documented rejection reversal.
- iii) Treatment of Acute rejection:
 - (1) Acute rejection will be treated per provider discretion.
- iv) Opportunistic Infections

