- d) Missing data and imputation methods
 - i) Under the intention-to-treat principle, all subjects are included in the analysis. Extensive efforts will be made to keep all missing data to a minimum and minimize loss to follow-up (LTFU). However, it is likely that some missing data may occur.
- e) Data Handling and Record Keeping
 - i) In order to protect subjects against any risk regarding loss of personal information, all obligations under the Health Portability and Accountability Act (HIPPA) will be met. Additionally, all data will be collected and stored through the secure network server and behind the MUSC firewall. We will use electronic CRF forms to gather all study information (redcap.musc.edu). Data will only be stored on campus computers under the MUSC secure network. Data collection forms will be maintained within an office, which is a locked office facility on campus. Only approved study members will have access to patient data.
 - ii) Any data or information shared for dissemination will be de-identified and the confidentiality of all participants will be strictly maintained. The only persons with access to protected health information (PHI) will include study investigators, research coordinators and those approved by the MUSC IRB. All data will be secured on MUSC servers, behind firewalls, with passwords protecting entry in these systems. All PHI will be obtained and managed in accordance with the HIPAA Privacy Rule (45 CFR Parts 160 and 164).

13) Provisions to Monitor Data and Ensure Subject Safety

- a) Study modification/discontinuation
 - (1) The study may be modified or discontinued at any time by the IRB, the sponsor, the OHRP, the FDA, or other government agencies as part of their duties to ensure that research subjects are protected.
 - (2) After 16 subjects have been randomized and completed follow-up, efficacy and safety endpoints will be reviewed by a blinded Safety Monitor to identify if the risk profile is as expected. If significantly increased risk is identified in either or both arms of the study, sufficient to increase the risk over the potential benefit of the study, the study will be discontinued. Examples are included below:
 - (a) A 6-month rejection rate difference between arms > 20%
 - **(b)** A difference in grade 3 or higher infections (based on CTCAE) between arms of > 20%
 - (c) A graft loss difference between arms > 20%

b) Adverse Events

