 - i) AEs and SAEs will be reported in accordance with the FDA Guidelines for Post-Marketing Reporting of Adverse Events 21 CRF 314.80 and 21 CRF 600.80 http://www.fda.gov/medwatch/report/regs.htm. Any serious adverse event or a non-serious adverse event that is related to the study and unexpected will be reported to the FDA, per reporting guidelines, as soon as possible, but no later than 15 working days. Further, all serious adverse events that are related to the study and are unexpected must be reported to The Medical University of South Carolina IRB within 10 days per The Medical University of South Carolina IRB Unanticipated Problems and Adverse Events Policy and Procedures reporting guidelines.

14) Withdrawal of Subjects

- a) Criteria for intervention discontinuation
 - (1) The intervention will be withheld/discontinued for AE of grade 3 or higher or if requested by the study participant.
 - (2) Additionally, the intervention will be discontinued if the subject meets criteria for the following reasons:
 - (a) Loss of graft: Defined as death or need for retransplant. Patients will be deemed a treatment failure and the intervention will be discontinued.

15) Risks to Subjects

- a) An increased risk of getting some kinds of cancer, including skin and lymph gland cancer (lymphoma)
- b) An increased risk of infections. As immediate release tacrolimus can lower the ability of the immune system to fight infections, serious infections can happen in people taking immediate

release tacrolimus that can cause death. Patients should call their doctor right away if they have symptoms of an infection such as fever; sweats or chills; cough or flu-like symptoms; muscle aches; or warm, red, or painful areas on their skin

- c) High blood sugar (diabetes)
- d) Kidney injury and decreased kidney function
- e) Nervous system problems including encephalopathy, delirium, seizures, coma, tremors, paresthesia, headache, mental status changes, and changes in motor and sensory functions
- f) High levels of potassium in the blood (potassium is important for nerve and muscle function)
- g) High blood pressure
- h) Heart problems (myocardial hypertrophy)
- i) The most common side effects for Envarsus® Daily and Tacrolimus IR in people receiving kidney transplant are

En	ıvarsus XR	Tacrolimus IR	
Infection	70%	65%	
Tremors	19%	17%	
High Blood Pressure	23%	23%	
Kidney Problems	10%	10%	
Constipation	18%	25%	
Diarrhea	31%	34%	
Headache	15%	10%	
Trouble Sleeping	13%	11%	

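### Liver/kidney recipients are eligible, but kidney-graft rejection, and kidney-graft failure not judged to need retransplant, are not counted in the named rejection and graft-loss outcomes or the matching stopping examples

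*Combined protocol and SAP*

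**What the plan says.** Eligibility (Section 5 ii) (1)) covers adults "with a history of liver or liver/kidney transplant within 15 days to 12 months of transplant", and Section 8 recruits from the same two groups.

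Section 11 ii) (1) gives the only definition of rejection: "Acute rejection is defined as a liver allograft biopsy showing RAI 5 or greater". Section 11 i) (2) (c) adds: "Rejection and infection events will be recorded, as defined in the protocol". Rejection reversal is "return of liver function tests to within 20% of baseline and/or histologic clearance by Banff Criteria", and recurrence is counted from documented reversal.

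The same RAI threshold of 5 appears in the time-to-event outcome (Section 1 c) vi)), the treatment-failure outcome (Section 4 iii) (1)) and exclusion 5. The only biopsy to which the protocol ties that score is a liver biopsy. No definition of kidney-graft rejection appears anywhere.

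Graft loss is defined once, under the discontinuation criteria in Section 14 a) (2) (a): "Loss of graft: Defined as death or need for retransplant". No organ is named, and kidney-graft failure or dialysis is not mentioned.

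Section 13 a) (2) has a Safety Monitor review the data after 16 subjects have completed follow-up. Its first listed example for stopping is "A 6-month rejection rate difference between arms > 20" per cent. The others are the same margin for grade 3 or higher infections and for graft loss.

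**The concern.** The definitions do not match the population. The protocol knowingly admits patients who carry two grafts and then defines rejection on one of them. Because rejection is to be recorded as the protocol defines it, a site following the text has no rejection event to enter when the kidney graft of a dual-organ recipient is rejected. This is a stated rule that misclassifies an eligible subgroup, not merely a detail left open.

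Rejection and graft loss are the protocol's own chosen safety outcomes. They are analysed as times to event, and two of the three numerical stopping examples rest on them. The quarterly data report in Section 12 a) also lists acute rejections. Each of these counts would be too low for any dual-organ recipient with a kidney-graft event, and the comparison between arms could be distorted in either direction.

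**Working it through.** The plan gives no figure to reproduce on this point. The check is a reading of the definitions, followed by simple counting at the interim review.

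**Step 1: how three kidney-graft events would be classified.**

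1. *Biopsy-proven kidney rejection, graft retained.* Section 11 requires a liver biopsy, so this is not a rejection. There is no retransplant need, so it is not graft loss. It is recorded as an adverse event, or a serious one if, for example, the patient is hospitalised. MDRD may fall.
2. *Kidney-graft failure, judged to need a kidney retransplant.* Section 14 names no organ, so this may count as graft loss. The text is ambiguous.
3. *Kidney-graft failure on dialysis, not judged to need retransplant.* This meets neither part of the Section 14 wording and is not graft loss. It is recorded as an adverse or serious adverse event and would bear on MDRD.

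Case 1 is missing from the rejection outcomes and, if the Section 11 definition is applied, from stopping example (a). Case 3 is missing from graft loss and from example (c).

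**Step 2: weight of one event at the interim review.** Inputs: 16 completers and 1:1 allocation (Sections 13 and 10), hence 8 per arm if balanced; example threshold above 20 points.

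- One event: 1/8 = 12.5 points. One versus none does not cross 20.
- Two events versus none: 2/8 = 25 points, which crosses.
- So one liver rejection versus none reads 12.5. If an uncounted kidney rejection also occurred in that arm, the full count would read 25.
- In the other direction, two liver rejections versus none reads 25. One uncounted kidney rejection in the other arm would make it 2/8 − 1/8 = 12.5.
- With a 9/7 split the pattern holds: single events are 1/9 = 11.1 and 1/7 = 14.3 points; two versus none is 2/9 = 22.2 or 2/7 = 28.6.

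**Step 3: how many patients could be involved.** The documents do not give the share *p* of liver/kidney recipients. For assumed values, the expected number among 30 is 30*p*. In a given arm of 8, P(at least one) = 1 − (1 − *p*)^8 and P(at least two) = 1 − (1 − *p*)^8 − 8*p*(1 − *p*)^7.

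- *p* = 5%: 1.5 patients among 30; 34% and 6%.
- *p* = 10%: 3.0 patients; 57% and 19%.
- *p* = 15%: 4.5 patients; 73% and 34%.

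These are chances of enrolling such patients, not of missing events. If, purely for illustration, 20% of them had a kidney rejection, the per-patient chance would be 0.05 × 0.20 = 0.01 to 0.15 × 0.20 = 0.03. The chance of two or more missed events in a given arm of 8 is then 1 − 0.99^8 − 8(0.01)(0.99^7) ≈ 0.3% to 1 − 0.97^8 − 8(0.03)(0.97^7) ≈ 2%. A missed kidney event combining with a counted liver event is a further route, not included in that figure.

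**The case against.** Four stronger readings are tempting, and the documents support none of them.

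- *Kidney-graft events escape the safety endpoints altogether.* They do not. Adverse and serious adverse events are components of the safety outcome in Section 4 iii) (1), are compared between arms under Section 1 c) vii), and are defined in Section 13 without organ limits. Change in MDRD is an outcome in its own right, and hospitalisations, AEs and SAEs are reviewed quarterly.
- *Graft loss is liver-only.* The text says "Defined as death or need for retransplant" and names no organ, so a needed kidney retransplant can be read as included. Only failure without that need is clearly left out.
- *The stopping review is blind to the kidney.* The criterion is a significantly increased risk, judged on efficacy and safety endpoints, and the 20% differences are labelled examples. Example (a) does not itself repeat the RAI definition. The Safety Monitor could act on kidney-graft events reported as SAEs.
- *Under-immunosuppression is the main risk of changing formulation.* The documents do not say so. Section 2 reports similar Cmin and less variability after conversion, and both arms share a 3-10 ng/mL trough goal. The point does not need this premise.

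It is also fair to say that these are exploratory outcomes in a 30-patient neurotoxicity trial and that few patients may be affected.

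What remains is that the fallback is non-specific. The treatment-failure outcome includes any adverse event, so a kidney rejection looks the same there as a minor complaint. The time-to-event analyses gain nothing from AE capture. MDRD is a baseline-to-six-month change, not an event, and the Chem-7 panel is optional at every visit in the Section 10 schedule, although Section 11 v) requires it at end of treatment. The 20% examples are the only numerical guidance the reviewer is given.

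**Conclusion.** The point holds in a limited form. Kidney-graft rejection is absent from the named rejection outcomes and, under the protocol's definition, from stopping example (a). Kidney-graft failure not judged to need retransplant is absent from graft loss and example (c). Both are still captured non-specifically.

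One uncounted event is worth 12.5 points at a balanced 16-completer review. On its own it does not cross 20 points; it matters only in combination with other events. The number of missed events cannot be stated. The 5-15% share is an assumption, and the resulting 1.5 to 4.5 patients are enrolled liver/kidney recipients, not missed events.

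The primary and secondary analyses are untouched. This is a worthwhile, inexpensive correction to safety counting, not a flaw that threatens the trial's main result.

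**What to change.** For endpoint counting only:

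- In Section 11 ii) (1), the rejection and graft-loss outcomes in Sections 1 and 4, and the matching examples in Section 13 a) (2), state which graft each definition covers.
- For liver/kidney recipients, add a kidney-graft component: biopsy-proven kidney rejection from clinically indicated biopsies, and kidney-graft failure.
- Report liver and kidney events separately as well as combined, with one CRF field for the organ.
- Make the reversal and recurrence definitions consistent with this, since reversal now refers to liver function tests or Banff histology without naming the graft.

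Leave the Section 14 discontinuation rule as it stands; its graft-loss wording also governs treatment, so the endpoint definition should be written separately. For exclusion 5, ask only that the sponsor reconcile its wording with the eligible population; rewriting it would create a new eligibility rule.

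The cost is wording and one data field, with no added procedures. The downside is that rejection becomes a two-organ outcome on different grading scales, which reporting each organ separately handles.

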 - (1) Opportunistic infections will be defined as outlined in Appendix F
- v) Intervention Discontinuation Evaluations: At the scheduled time of intervention discontinuation (EOT, last date of study), the following evaluations must be completed: clinical assessment, CBC, CHEM-7, LFTs, Tacrolimus CO. In case of subject withdrawal from study, the patient will return to standard of care medications and request to continue with final assessment using PGI-I, IMAB-Q 10, MSVT, MoCA, SF-12, MMSE, and FTM (if applicable) will be discussed with a qualified team member.

12) Data Management

- a) Data management will be overseen and data analysis will be independently reviewed by an Investigator on the study who has no related financial interest. This member will serve as independent monitor to oversee data collection and management, and to verify the integrity of data and interpretation of study results. Data reports, including patient recruitment and randomization numbers, clinical outcomes (acute rejections, infections and hospitalizations), AEs and SAEs will be reviewed quarterly.
- b) Dichotomous data will be analyzed using Chi Square or Fischer Exact, when appropriate, and continuous data points will be analyzed using Student's t-test or Mann Whitney U, for parametric and nonparametric data, respectively.
- c) Sample size estimation for the primary outcome
 - i) The proposed sample size (n=30) would be able to demonstrate a mean difference in neurologic toxicity burden, using the Patient Global Impression of Improvement (PGI-I) rating of 20 ± 15 with greater than 80% power using a two-tailed t-test with an alpha set at 0.05. Based on reported neurologic toxicities from the literature (headache 64%, insomnia 64%, tremor 56%, paresthesia 40%), a mean score of 45 is expected at baseline. Using the independent samples t-test comparing two groups with a two-sided significance level of

0.05, a sample size of 14 subjects per group would be required to obtain a power of at least 0.8 if the two groups have a mean of 25 ± 15 neurologic toxicity burden in the Envarsus cohort at the conclusion of the study and mean of 45 ± 20 neurologic toxicity burden at baseline and follow up in the tacrolimus IR group. Estimating a 10% drop out rate, we propose a sample size of 15 subjects per group. This sample size will provide adequate power to show a statistical and clinical difference in the neurologic toxicity burden between the two groups.

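### Sections 11 v and 14 do not separate stopping study drug from leaving the study, so the day-180 PGI-I is not secured for subjects who stop early

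*Combined protocol and SAP*

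**What the plan says.** Five places in the combined protocol and SAP bear on this.

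- **Section 14 (Withdrawal of Subjects)** contains only criteria for discontinuing the intervention: "The intervention will be withheld/discontinued for AE of grade 3 or higher or if requested by the study participant". Graft loss is listed separately. It does not say whether such subjects stay in follow-up.
- **Section 11 v (Intervention Discontinuation Evaluations)** first covers planned completion: "At the scheduled time of intervention discontinuation (EOT, last date of study". The evaluations it makes mandatory then are the clinical assessment and laboratory tests; the PGI-I is not among them. For an unscheduled exit it says: "In case of subject withdrawal from study, the patient will return to standard of care medications and request to continue with final assessment". The scales are then named, and the matter is to be discussed with a team member. No date is given.
- **Section 3** defines standard of care as tacrolimus IR twice daily with or without an adjunctive agent and prednisone, which is also Arm 1. It plans six months of follow-up or until a terminal end point, a term it does not define.
- **The schedule in Section 10 f** marks the PGI-I as required at baseline and at day 180±10, and at no visit between.
- **Section 12 d** says: "Under the intention-to-treat principle, all subjects are included in the analysis". Its heading refers to imputation methods, but the text names none.

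**The concern.** Sections 11 v and 14 each carry the other's label. A coordinator whose patient stops study drug under Section 14 finds no rule for a subject who is off drug but still in the study. The nearest instruction is the withdrawal sentence in Section 11 v. Applied to that patient, it turns a required day-180 measurement into an undated request.

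With one scheduled post-baseline PGI-I, a missed final assessment leaves no change score. The tests named in Section 12 b (t-test or Mann-Whitney) use only subjects who have a value, so without a stated rule the analysis becomes a completer comparison by default. A PGI-I taken at the time of stopping, if later used as the six-month value, would reflect a different exposure time.

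The stopping trigger is broad. Section 13 b defines adverse events regardless of cause, and the grade 3 rule in Section 14 carries no relatedness condition. Returning to standard of care changes the drug only for Envarsus subjects, and the trial is open-label, so early exits may well be more common in that arm.

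**Working it through.** **Inputs from Section 12 c.** The test is planned "using a two-tailed t-test with an alpha set at 0.05". The assumptions are "a mean of 25 ± 15 neurologic toxicity burden in the Envarsus cohort" and "mean of 45 ± 20 neurologic toxicity burden at baseline and follow up in the tacrolimus IR group", so the difference is 45 − 25 = 20. The stated result is "a sample size of 14 subjects per group would be required to obtain a power of at least 0.8". Enrolment is 15 per arm, with 10% dropout assumed.

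**The plan's own figure.** Root-mean-square SD = √((15² + 20²)/2) = 17.68. The noncentral t gives n = 13.3, so 14 per group, with power 0.82. The stated figure reproduces. At the enrolled 15 per arm, power is 0.85.

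**Illustration. The assumptions are not in the documents:** m of the 15 Envarsus subjects stop early, and a stopper scores like a control subject (45, SD 20). The documents give no stopping rate, so m = 1 to 3 is shown. Let p = m/15.

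- As-randomised difference = 20 × (1 − p).
- Envarsus-arm variance = (1 − p) × 225 + p × 400 + p(1 − p) × 20². For m = 3 this is 180 + 80 + 64 = 324, so the SD is 18.0.
- Power is from a two-sided Welch t-test (noncentral t) with control SD 20 and 15 per arm.
- If stoppers are left unassessed and dropped, the expected difference stays at 20 with 15 − m Envarsus subjects.

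| m | As-randomised difference | Power, all assessed | Completer difference | Power, stoppers dropped |
|---|---|---|---|---|
| 0 | 20.0 | 0.85 | 20 | 0.85 |
| 1 | 18.7 | 0.77 | 20 | 0.84 |
| 2 | 17.3 | 0.69 | 20 | 0.83 |
| 3 | 16.0 | 0.60 | 20 | 0.81 |

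The completer result therefore overstates the as-randomised difference by 1.3, 2.7 and 4.0 points for m = 1, 2 and 3. In relative terms, 20/18.7 is 7% too large and 20/16 is 25% too large. At the plan's own 10% dropout rate the as-randomised difference would be 20 × 0.9 = 18, and 20/18 is 11% too large.

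The sample size allows for lost headcount only, not for subjects who switch back to the control regimen and are still analysed in the Envarsus arm.

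**The case against.** The strongest reply is that the sentence in Section 11 v governs withdrawal from the study, not stopping drug. Section 3 still calls for six months of follow-up, and the schedule requires the day-180 PGI-I with no exception for drug stoppers. On that reading a stopper still owes the measurement, and Section 11 v is a retention provision that seeks data even from people who have left. A subject who withdraws consent cannot be compelled. All of this stands. What remains is that no sentence says a Section 14 stopper stays in the study, and the two headings point the other way.

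Four stronger readings are tempting, and the documents do not support them.

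- *The intention-to-treat analysis cannot be delivered.* Returning to tacrolimus IR dilutes the effect but does not break analysis as randomised. The as-randomised difference of 16 in the illustration is a valid estimate. Section 12 d also promises extensive efforts to limit missing data, and no section plans a completer analysis.
- *Data will be lost in the Envarsus arm only.* Participant request, graft loss and study withdrawal can occur in either arm. How the grade 3 rule applies to a control subject is unstated, so a one-arm effect is a prediction.
- *Section 11 v equates every end of treatment with the end of the study.* The phrase concerns the scheduled end, where the two coincide for a subject treated as planned.
- *An early exit PGI-I will be used as the six-month value.* Nothing provides for that. The final assessment most naturally means day 180; the text simply gives no date.

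The 25% figure needs 3 of 15 Envarsus subjects to stop, all to be unassessed, and all to score at the control mean. Section 14 also allows the drug to be withheld rather than discontinued, so not every grade 3 event ends treatment.

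Section 3 b could be read as placing the PGI-I at every visit. The schedule it points to does not, and no section says how interim scores would be used.

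**Conclusion.** The gap is real but limited: the plan should be fixed here, and it is not unworkable as it stands. Sections 11 v and 14 do not distinguish stopping study drug from leaving the study, and the only instruction for an unscheduled exit makes the sole post-baseline primary measurement an undated request. That fits poorly with Section 3, the schedule and Section 12 d. The intention-to-treat comparison is not secured; it is not ruled out. Loss is possible in both arms and likely greater on Envarsus, because only those subjects change drug on stopping and the trial is open-label.

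The size depends on a stopping rate that the documents do not give and on stoppers scoring like controls. Under those assumptions, one to three unassessed Envarsus stoppers would inflate the apparent difference by 1.3 to 4.0 points on an assumed 20. Assessing them removes that bias but exposes the dilution, with power of about 0.77 to 0.60.

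**What to change.** Leave the clinical stopping rule as it is and change the follow-up wording.

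- State in Sections 11 v and 14 that stopping study drug is not withdrawal from the study.
- Require the PGI-I, and the FTM if applicable, at day 180±10 from every randomised subject who has not withdrawn consent, whatever drug they are taking, and analyse each in the assigned arm.
- State that an assessment made at the time of stopping is additional and never replaces day 180.
- Record the date of and reason for stopping. Section 11 i already records immunosuppressant doses, and Section 13 b the action taken on study treatment after an adverse event, so little is new.
- Reconcile Sections 3, 11 v, 12 d and 14, including how the grade 3 rule applies to a control subject.

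No new procedure is needed: the schedule footnotes already provide the PGI-I as a REDCap survey and the FTM by video visit. The cost is some coordinator effort to keep stoppers in follow-up, and an estimated effect that may be smaller than a completer estimate. This wording does not settle how subjects who do withdraw consent enter the analysis; Section 12 d still has to name a method for them.
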